1.0 BACKGROUND AND RATIONALE

1.1 Study Disease

Nephrolithiasis is a relatively common affliction, affecting upwards of 10% of the US population and accounts for a significant number of Emergency Department (ED) visits [1]. Computed tomography (CT) is the gold standard for evaluation of acute renal colic and diagnosis of urolithiasis [2] [3]. Recently, the use of CT has come under scrutiny due to ionizing radiation and its attendant risks, including skin injury, cataract formation, and most worrisome, solid and hematological malignancy [3][4, 5]. Furthermore, radiation exposure is increased in obese patients [6], a known risk factor for stone disease. Also, as many patients have a life-long affliction with nephrolithiasis[1], the potential for a considerable aggregate accumulation of radiation exposure over their lifespan can be excessive [5, 7, 8]. This patient population, especially those first diagnosed at a young age, would benefit from imaging modalities that do not involve radiation.

Therefore, various efforts are being made to reduce this radiation exposure. One of the most common types of imaging used in the evaluation of nephrolithiasis as an alternative to CT is renal and bladder ultrasound (RBUS) [9]. RBUS has largely been used as an adjunct study in the management of patients with nephrolithiasis[10], especially during pregnancy and in pediatric stone formers. Due to its relatively low cost and lack of radiation, it has the potential to have an increasingly prominent role. The incorporation of ureteral jets assessment (UJA) when using RBUS to assess patients with nephrolithiasis has been shown to have added diagnostic and possibly also prognostic value in the evaluation of these patients[10]. Several studies have attempted to assess the exact role of UJA in patients with nephrolithiasis but have had limited success in delineating its exact role in the treatment algorithm [11].

The prognosis of a ureteral stone as can be conveyed to the patient is based on a historical study from Miller and Kane. In 1999, the authors studied 75 patients with ureteral stones ranging from less than 2mm to 10mm over approximately 6 weeks' time. It was found that smaller, more distal stones pass sooner and that stones <4mm pass 95% of the time, although this may take up to 40 days [13]. Since that time, multiple studies have shown medical expulsive therapy (MET) to be effective for earlier stone passage [14, 15, 16]. No modern investigation of stone passage rates based on size has been performed in the MET era.

1.2 Rationale

Due to the increasing use of CT and concern for radiation exposure, it is important to consider alternative diagnostic imaging modalities. We seek to evaluate patients who present to the Barnes-Jewish Hospital (BJH) ED and to the Urology office with renal colic who have been diagnosed with a ureteral stone. We seek to determine whether the findings on ureteral jet assessment (UJA) by RBUS are predictive of a patient's clinical outcome. Specifically, we seek to

evaluate whether the presence, absence or relative strength of the ipsilateral ureteral jet can predict spontaneous passage versus need for surgical intervention over a 42-day (6-week) time period. As many patients have a life-long affliction with nephrolithiasis[1], the potential for a considerable aggregate accumulation of radiation exposure over their lifespan can be excessive and should not be overlooked [5, 7, 8]. This patient population, especially those first diagnosed at a young age, would benefit from imaging modalities that do not involve radiation.

Evaluating the significance of UJA and RBUS in patients with renal colic will help define the role of this imaging modality, as an alternative to ionizing radiation-based studies. The prognosis of urolithiasis based on UJA will be defined, as well as the natural history of stones managed expectantly. We hypothesize that UJA showing weak or absent ureteral jet will predict obstruction and a higher rate of surgical treatment compared to spontaneous passage. We hypothesize that larger stones will be less likely to pass without surgical intervention.

2.0 OBJECTIVES

2.1 Primary Objective

1. To determine whether use of renal bladder ultrasound (RBUS) with UJA is predictive of spontaneous stone passage versus need for surgical intervention over a 42-day time frame.

2.2 Secondary Objectives

1. To determine whether RBUS with UJA, in conjunction with standard of care history, physical examination and laboratory studies confers the same diagnostic information as the gold standard, non-contrast CT.
2. To determine the natural history and rate and time of stone passage for ureteral stones of differing locations (proximal, mid or distal ureter) and sizes (<2mm, 2-4mm, 5mm, 6-7mm, 9-10mm).

3.0 PATIENT SELECTION

3.1 Inclusion Criteria

Patients must meet all of the following inclusion criteria to be eligible for study participation:

1. Age 18 and older at the time of consent
2. Willing and able to sign consent
3. CT diagnosis of ureteral stone with a stone burden less than or equal to 10mm

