3.2 Exclusion Criteria

Patients must not meet any of the following exclusion criteria to be eligible for study participation:

1. Obstructed solitary kidney
2. Obstructed transplant kidney
3. Bilateral obstructed kidneys
4. Any condition or reason that, in the opinion of the treating physician, interferes with the patient's ability to participate or places the patient at undue risk.

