5.2 Study Plan and Procedures

Study RBUS with UJA will be obtained within 10 days following CT diagnosis of ureteral calculus. Ureteral jet data will be documented and patients will be followed prospectively for 42 days at 2 weeks, 4 weeks and 42 days (6 weeks) after diagnostic CT. Specifically, patients will be followed for spontaneous stone passage and will be expected to record date of stone retrieval. If specific date of stone passage is not known, date of standard of care imaging confirming absence of stone(s) will be used as the date of stone passage. If spontaneous stone passage is not achieved, patients will be counseled regarding further standard of care treatment options including surgical stone removal. If surgical intervention is indicated, time to surgical procedure will also be recorded. This patient cohort will be analyzed retrospectively to determine whether RBUS with UJA is predictive of spontaneous stone passage versus need for surgical intervention over a 42-day period.

Interpretation of RBUS and UJA:

Abdominal radiologists will interpret the RBUS research reads. All grey scale and color Doppler examinations will be performed by means of a commercially available unit with a 1-5 MHz phased array transducer or a 1-6 curved transducer. Flow toward the transducer is assigned a red color on Doppler. For grey scale evaluation, the presence or absence of urinary tract stones, size (longest axis in mm) and location- R, L, upper pole, interpolar and lower pole of the kidneys, proximal ureter, distal ureter and bladder- will be documented. The level of the renal pelvis represents the interpolar kidney with upper and lower pole above and below this level. For this study, a urinary tract stone will be termed an echogenic focus that demonstrates either posterior acoustic shadowing and or twinkle artifact on color Doppler images. In addition, presence of hydronephrosis (mild, moderate, and severe) will be documented. For the purpose of this read, hydronephrosis will be defined as such: mild hydronephrosis - urine fills the intra and extra renal pelvis and the major calyces are dilated; moderate hydronephrosis – above + dilatation of the minor calyx with preservation of the renal parenchyma; severe hydronephrosis – above +

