5.3 Study Follow-up

After study RBUS is obtained, patients will be followed prospectively by telephone call at 2 weeks, 4 weeks and 42 days (6 weeks) from the time of diagnostic CT. They will be followed for spontaneous stone passage, and be asked to keep record of when this occurs. During the 42-day follow up, their course will also be monitored for ED visits, surgical intervention and hospital admissions. All currently available medical records such as Clindesk, Allscripts, Compass, HMED will be reviewed retrospectively to follow participants' clinical course, specifically to determine the need for surgical intervention or spontaneous stone passage. Billing records may also be used to identify patients who underwent surgical intervention based on CPT codes. Evaluation of the patient's emergency room records with a focus on their presenting symptomatology and initial evaluation by the emergency provider will be performed. Any additional laboratory tests and/or imaging obtained during their emergency room or office visit will also be reviewed and collected for study purposes.

Surgical intervention, including ureteral stent or nephrostomy tube placement, ureteroscopy/laser lithotripsy, or extracorporeal shockwave lithotripsy (ESWL) will be instituted, as per standard of care. A follow up telephone call at 2 weeks, 4 weeks and 42

days (6 weeks) from the time of diagnostic CT will be performed in case of care received outside of the Barnes-Jewish Hospital (BJH) system and medical records reviewed for ER visits, hospital admissions and surgical intervention.

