APPENDIX A: Study Schedule of Events

		Post-Enrollment Assessment and Follow-up		
		Within one day of diagnostic CT	2 weeks post diagnostic CT (+/- 2 days)	4 weeks post diagnostic CT (+/- 2 days)
Informed Consent	X			
Incl./Excl. Criteria Confirmation	X			
RBUS with UJA	X			
Demographics¹	X			
Medical & Surgical History¹	X			
Height & Weight¹	X			
Basic metabolic panel¹	X			
Complete blood count¹	X			
Urine analysis and microscopy¹	X			
CT scan¹	X			
Assessments:				
Study related AEs/reportable events		X	X	X
Clinical stone management¹		X	X	X
Passage of stone		X	X	X

¹ as part of standard clinical care.

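### No rule separates patients whose surgery or drainage was already decided on the CT from those on a trial of passage, so the primary comparison can count interventions chosen before the ultrasound

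*Combined protocol and SAP*

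**What the plan says.** Section 3.1 has three criteria: age, consent and a "CT diagnosis of ureteral stone with a stone burden less than or equal to 10mm". The exclusions in section 3.2 are an obstructed solitary kidney, an obstructed transplant kidney, bilateral obstruction, and a discretionary clause for any condition or reason that "interferes with the patient's ability to participate or places the patient at undue risk". None refers to planned management.

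The aims are worded for patients who are waiting to see whether the stone passes. Section 1.2 promises to define the prognosis by UJA "as well as the natural history of stones managed expectantly". Section 2.1 asks whether ultrasound with UJA "is predictive of spontaneous stone passage versus need for surgical intervention over a 42-day time frame". Section 5.2 describes the expected course: "If spontaneous stone passage is not achieved, patients will be counseled regarding further standard of care treatment options including surgical stone removal".

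The order of events is CT, then consent (section 5.1), then the study ultrasound: "Study RBUS with UJA will be obtained within 10 days following CT diagnosis of ureteral calculus". Appendix A heads the corresponding column "Within one day of diagnostic CT". These two timings need to be reconciled, but under either one the CT comes first.

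Section 5.3 defines the event broadly: "Surgical intervention, including ureteral stent or nephrostomy tube placement, ureteroscopy/laser lithotripsy, or extracorporeal shockwave lithotripsy (ESWL) will be instituted, as per standard of care". Section 7.3 applies a chi-square test and logistic regression to intervention, and Kaplan-Meier curves and a Cox model to time to passage. It specifies no subset of the enrolled cohort. The covariates it names are age, gender, BMI, side, stone size and stone passage.

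**The concern.** For a patient whose procedure was settled on the CT and the presentation, the jet finding cannot forecast the decision, because the decision came first. This differs from surgery done before the scan and from a scan that influences the surgeon. Here the procedure follows the scan but was chosen before it.

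The section 1.2 hypothesis is that weak or absent jets signal obstruction. If obstruction or size also drives early decisions for surgery, pre-decided patients gather in the weak or absent jet group and raise its intervention rate, whether or not UJA says anything about patients who are waiting. If the decisions have nothing to do with jets, they add the same block of events to both groups and shrink a real difference.

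These patients also have little or no chance to pass the stone. In secondary objective 2 the proportion passing, by size and location, is therefore lowered in either case, and most in any category where early surgery is most common.

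As far as the Appendix A table can be read, the baseline items do not include the management plan in force before the scan; clinical stone management is marked only at follow-up. The analyst would then have no field with which to separate the two kinds of event.

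**Working it through.** **The plan's own figure.** Section 7.2 gives a target of about 100 participants. Section 7.3 mentions an initial power analysis but states no alpha, power, effect size or event rates, so the target cannot be reproduced. Every rate below is an assumption.

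**Inputs.** Total 100 (section 7.2), assumed to split 50:50 into weak or absent jets and jets similar to the other side. Section 5.2 defines three jet groups and section 7.3 compares two; this grouping is assumed. The test is a two-sided 5% uncorrected chi-square, with rejection probabilities from exact binomial enumeration. Let q be the share with surgery or drainage already decided, and r the later intervention rate among the rest. The observed rate is p = q + (1 − q) × r.

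**Case 1: UJA has no effect (r = 15% in both groups).**

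| q, weak/absent vs similar | p, weak/absent | p, similar | Risk ratio | Rejection |
|---|---|---|---|---|
| 10% vs 10% | 0.10 + 0.90 × 0.15 = 23.5% | 23.5% | 1.00 | about 5% |
| 10% vs 5% | 23.5% | 0.05 + 0.95 × 0.15 = 19.25% | 1.22 | about 8% |
| 20% vs 10% | 0.20 + 0.80 × 0.15 = 32% | 23.5% | 1.36 | about 16% |
| 30% vs 10% | 0.30 + 0.70 × 0.15 = 40.5% | 23.5% | 1.72 | about 45% |
| 40% vs 10% | 0.40 + 0.60 × 0.15 = 49% | 23.5% | 2.09 | about 77% |

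If the comparison is restricted to patients on a trial of passage, q = 0 in both groups, both rates are 15%, and rejection returns to about 5%.

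**Case 2: UJA has a real effect and planned surgery is unrelated to jets.** Take 40% versus 20% among patients on a trial of passage, with q = 20% in both groups.

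- All enrolled: 0.20 + 0.80 × 0.40 = 52% versus 0.20 + 0.80 × 0.20 = 36%. The difference shrinks from 20 to 16 points.
- Power with 50 per group: about 60% with no pre-planned patients, and about 38% with them left in.
- Power with them excluded (50 × 0.80 = 40 per group, 40% versus 20%): about 50%.

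**Case 3: passage proportions.** If a proportion s passes the stone under a trial of passage, and pre-planned patients are treated before passing, the crude proportion is (1 − q) × s. With q = 10% or 20%, it is a tenth or a fifth lower in relative terms, whether or not q is related to jets.

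**The case against.** The strongest reply is that the expectant-management wording in section 1.2 belongs to the natural-history aim. The primary objective contrasts passage with need for surgery and does not say among whom. The study also looks for an alternative to CT, so it is relevant if UJA picks out the patients whom CT sends to surgery. This stands in part: a restricted set answers a narrower question. But agreement with CT-based diagnosis and treatment is secondary objective 1, where all participants remain. The primary objective is about prediction over 42 days, and section 5.2 describes surgery counselling as following failure to pass.

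A reader might infer that pre-booked patients will be enrolled in number, or that any association found would be spurious. The documents support neither. They say nothing about how many such patients there would be, and section 3.2 already removes several obstructed presentations. The discretionary exclusion could remove a few more, although a booked procedure does not in itself prevent an ultrasound. The direction is also not fixed, since planning unrelated to jets dilutes rather than inflates.

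The larger figures in Case 1 need a marked imbalance that nothing in the documents establishes; with 10% versus 5% the excess over the nominal 5% is small. Stone size is in the logistic model, which removes part of any size-driven bias there. It does not remove the part due to obstruction or clinical state, and it does nothing for the chi-square test.

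Finally, restriction costs patients when recruitment is already described as difficult. In Case 2, however, excluding them gives more power than keeping them (about 50% against 38%).

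**Conclusion.** The point holds as a gap in the analysis-set definition. As written, the plan allows interventions decided on the CT to be counted as outcomes that UJA predicted, and no section flags or separates them.

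The size cannot be known from the documents. Under the assumed 15% later intervention and 50 per group, the false-positive rate runs from about 8% to about 77% over the imbalances shown, and is about 5% when the shares are equal. With equal shares the harm is lost power. Crude passage proportions in secondary objective 2 are lowered in either case. The restriction helps whichever way planned surgery relates to jets, which is why the change is worth making without knowing the rates. The point does not show that the eligibility criteria are wrong.

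**What to change.** On the enrolment form, before the ultrasound, record the treating clinician's management plan in force: trial of passage, or surgery or drainage already planned. For participants already enrolled, abstract it from ED or urology notes dated before the scan; section 5.3 already provides for review of ED and medical records.

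In section 7.3, define the analysis set for the primary objective and secondary objective 2 as participants on a trial of passage at the time of the ultrasound. Report the all-enrolled result as a sensitivity analysis, with the number pre-planned in each jet group. Keep all participants for secondary objective 1.

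The cost is one form field, some chart abstraction, a sentence or two in section 7.3 and a somewhat smaller primary analysis set. Eligibility and clinical management are unchanged.

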3.2 Exclusion Criteria

Patients must not meet any of the following exclusion criteria to be eligible for study participation:

1. Obstructed solitary kidney
2. Obstructed transplant kidney
3. Bilateral obstructed kidneys
4. Any condition or reason that, in the opinion of the treating physician, interferes with the patient's ability to participate or places the patient at undue risk.

3.3 Inclusion of Women and Minorities

Both men and women and members of all races and ethnic groups are eligible for this trial.

4.0 REGISTRATION PROCEDURES

The following steps must be taken before registering patients to this study:

1. Confirmation of patient eligibility
2. Assignment of unique patient number (UPN)

4.1 Assignment of UPN

Once enrolled in the study, each participant will be assigned a unique participant study number (study ID) which will not include participant's initials. Only research team members will have access to the master key linking participant number to identifiable information, which will remain secure in an encrypted, password-protected file or under two locks. Clinical research data will be identified by participant's unique study number and will also include identifiable information such as subject's name and date of birth. Only members of the research team will have access to participants' research data.

5.0 STUDY PLAN

5.1 Screening and Informed Consent

Subjects will be seen and counseled by either the attending ED physician or their Urologist as part of the normal course of practice. Patients may be approached about study participation as soon as ureteral stone is suspected based on clinical presentation. Following CT diagnosis of ureteral stone, study team will further discuss study participation with the patient and complete the consent process if the patient is willing to participate.

The discussion regarding study participation will take place in a private setting, such as in a private consult room, to maintain confidentiality. HRPO approved consent form will be used to guide the consent process and document participant's consent. During the consent

process, the study team will explain RBUS with UJA, the normal anticipated course of a patient with the represented stone burden, potential risks and benefits of study participation, compensation and study follow-up schedule. Patients will be encouraged to ask questions and discuss the study with family. They will be given ample time to review the consent. It is possible that some participants may be contacted by phone to assess their interest in this study. If the participant expresses interest in the study, informed consent form will be mailed/e-mailed to him/her. This will be done in an effort to allow the patient ample time to read the consent at home, consider the study and discuss it with friends and family. This will not replace the face-to-face consent discussion the research team will have with the patient prior to signing the consent form.

Patients may decline to participate without an impact on their care. They will not be pressured to participate. No study related procedures will take place prior to the completion of the informed consent process and participant signing the HRPO approved consent.

5.2 Study Plan and Procedures

Study RBUS with UJA will be obtained within 10 days following CT diagnosis of ureteral calculus. Ureteral jet data will be documented and patients will be followed prospectively for 42 days at 2 weeks, 4 weeks and 42 days (6 weeks) after diagnostic CT. Specifically, patients will be followed for spontaneous stone passage and will be expected to record date of stone retrieval. If specific date of stone passage is not known, date of standard of care imaging confirming absence of stone(s) will be used as the date of stone passage. If spontaneous stone passage is not achieved, patients will be counseled regarding further standard of care treatment options including surgical stone removal. If surgical intervention is indicated, time to surgical procedure will also be recorded. This patient cohort will be analyzed retrospectively to determine whether RBUS with UJA is predictive of spontaneous stone passage versus need for surgical intervention over a 42-day period.

Interpretation of RBUS and UJA:

Abdominal radiologists will interpret the RBUS research reads. All grey scale and color Doppler examinations will be performed by means of a commercially available unit with a 1-5 MHz phased array transducer or a 1-6 curved transducer. Flow toward the transducer is assigned a red color on Doppler. For grey scale evaluation, the presence or absence of urinary tract stones, size (longest axis in mm) and location- R, L, upper pole, interpolar and lower pole of the kidneys, proximal ureter, distal ureter and bladder- will be documented. The level of the renal pelvis represents the interpolar kidney with upper and lower pole above and below this level. For this study, a urinary tract stone will be termed an echogenic focus that demonstrates either posterior acoustic shadowing and or twinkle artifact on color Doppler images. In addition, presence of hydronephrosis (mild, moderate, and severe) will be documented. For the purpose of this read, hydronephrosis will be defined as such: mild hydronephrosis - urine fills the intra and extra renal pelvis and the major calyces are dilated; moderate hydronephrosis – above + dilatation of the minor calyx with preservation of the renal parenchyma; severe hydronephrosis – above +

thin renal parenchyma. In addition, the presence or absence of hydroureter (proximal ureter, above the iliac bifurcation and distal ureter, below the iliac bifurcation) will be documented. If there is a stone in the renal pelvis, it will be recorded as interpolar kidney and noted as renal pelvis. For any case, if the reader believes that a particular stone is the cause of the participant's symptoms, then this will be noted. This is particularly useful in cases in which there are multiple stones. The bladder will be examined in the transverse plane at the level of the trigone to view both jets simultaneously. All participants will be scanned for 5 minutes. The number of jets from each ureteral orifice will be tabulated over time so that ureteral jet frequency, defined as number of jets per minute, can be calculated. Patients will be categorized into three groups. Group I- no ureteral jets on the symptomatic side; Group II- continuous low-level ureteral jet on the symptomatic side; Group III- ureteral jets similar to nonsymptomatic side.

In order to determine if RBUS with UJA along with clinical data confers non-inferior information compared to non-contrast CT, objective findings such as laboratory data including BMP, CBC, urine analysis and physical exam obtained as part of routine care will be retrieved from the patient's medical record and reviewed retrospectively. Clinical data and RBUS results will be de-identified/coded and the Urologist will be blinded to the CT results. Diagnosis and treatment recommendations will be determined based upon these findings and compared to those attained by CT to assess for congruence. Statistical analysis will be performed to determine non-inferiority between the studies.

Stone size and location based on CT will be recorded at the time of enrollment into the study and time to stone passage will be recorded. All study participants will be followed for stone passage. Time to stone passage will be stratified according to stone location (proximal, mid or distal ureter) and size (<2mm, 2-4mm, 5mm, 6-7mm, 9-10mm).

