5.5 Duration of Follow-Up

Patients will be followed by telephone call at 2 and 4 weeks and 42 days (6 weeks) after diagnostic CT. They will have a clinic visit with their urologist per standard of care practice.

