6.0 DATA AND SAFETY MONITORING

Participation in the proposed study will not pose any risks to the participants beyond what is expected from the standard of care stone management.

The PI will monitor the study for any reportable events from the time of the study RBUS to day 42 post diagnostic CT. All HRPO guidelines for reporting events meeting defined criteria will be followed.

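### Section 7.3 sets no time zero and no rule for events between the CT and a UJA scan allowed up to 10 days later, so outcomes that precede the scan can be counted as predicted by it

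*Combined protocol and SAP*

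**What the plan says.** **Predictor.** Section 5.2: "Study RBUS with UJA will be obtained within 10 days following CT diagnosis of ureteral calculus".

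**Clock.** Section 5.5: "Patients will be followed by telephone call at 2 and 4 weeks and 42 days (6 weeks) after diagnostic CT". Sections 5.2 and 5.3 use the same origin. Section 5.3 reads "After study RBUS is obtained, patients will be followed prospectively by telephone call at 2 weeks, 4 weeks and 42 days (6 weeks) from" the diagnostic CT. It then adds a retrospective review of medical records for passage or surgery, with no start date for that review.

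**Eligibility.** Section 3.1 asks for "CT diagnosis of ureteral stone with a stone burden less than or equal to 10mm". Nothing in 3.1, 3.2 or the removal criteria in 5.6 requires the stone to be still present and untreated at the scan.

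**Analysis.** Section 7.3 names Kaplan-Meier and Cox for time to passage, and chi-square and logistic regression for intervention. It states no time origin, no delayed entry or landmark, and no handling of events before the scan.

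**The concern.** The primary objective (2.1) is prediction. A scan cannot predict a passage or an operation that has already happened. If time runs from CT and such patients are kept, a stone that passes on day 3 followed by a scan on day 8 enters the analysis as an early passage, grouped by jets seen through a ureter that is already clear. Section 5.2 defines Group III by jets resembling those on the other side, which is how a cleared ureter might look. The hypothesis in 1.2 is that weak or absent jets go with obstruction and more surgery, so this error would favour it. The false signal could also enter the interim analysis at 50 patients, which decides whether recruitment continues.

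**Working it through.** **Inputs from the documents.** Scan window 0 to 10 days (5.2); horizon 42 days from CT (5.2, 5.3, 5.5); about 100 participants (7.2). The documents give no alpha, cohort passage rate, scan-time distribution or rate of jet recovery. The power inputs behind the target of 100 are not shown, so there is no plan figure to reproduce.

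**Assumptions.** Exponential times; 42-day passage F of 50, 70 or 80%; two-sided 5% test; UJA has no prognostic value; stones in place split 50:50 between Group III and Groups I+II. That split is one reading of the two groups in 7.3, since 5.2 defines three.

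**Step 1: share passed before the scan.** With rate λ = −ln(1−F)/42 and scans uniform over 0 to 10 days, the share is 1 − (1−e^(−10λ))/(10λ).

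- F = 50%: 10λ = 0.165, share 7.8%
- F = 70%: 10λ = 0.287, share 13.1%
- F = 80%: 10λ = 0.383, share 16.9%

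With all scans inside one day the share is about 1 to 2%.

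**Step 2: how the bias arises.** Take F = 70% and let every passed stone read as Group III. Per 100 patients, 13.1 pass before the scan and 86.9 are split evenly, 43.45 to each side. The other 70 − 13.1 = 56.9 passages also split evenly, 28.45 each. Group III then shows (13.1 + 28.45)/(13.1 + 43.45) = 73.5% passage, and Groups I+II show 28.45/43.45 = 65.5%. An 8-point gap appears with no true effect, and all the pre-scan passages sit in Group III.

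**Step 3: false rejection by the log-rank test from CT** (n = 100, 10,000 simulated null trials per cell, Monte Carlo error up to 0.5 points).

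| Scan timing | Passed stones read as Group III | Attendance once passed | F=50% | F=70% | F=80% |
|---|---|---|---|---|---|
| Uniform 0–10 days | all | full | 18% | 29% | 38% |
| Uniform 0–10 days | all | half | 9% | 12% | 16% |
| Uniform 0–10 days | 70% | full | 7% | 9% | 11% |
| Uniform 0–10 days | 70% | half | 5% | 6% | 7% |
| Uniform 0–10 days | no recovery | full | about 5% | about 5% | about 5% |
| Uniform 0–5 days | all | full | 9% | 12% | 16% |
| 80% within one day | all | full | 6% | 7% | 9% |
| All within one day | all | full | 5.2–5.6% across F | | |

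A repeat of the fourth row gave about 6 to 8%, hence the 5 to 8% quoted for that case. In the first row the spurious rate ratio is 1.35, 1.41 and 1.47.

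**Step 4: chi-square on intervention, all events from CT.** Scans are uniform over 0 to 10 days with full attendance. Ranges cover assumed 42-day passage/intervention of 50/30, 70/20 and 80/10%.

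| Passed stones read as Group III | Treated sides never Group III | Half | Always |
|---|---|---|---|
| 100% | 32–51% | 11–15% | 5–6% |
| 70% | 18–29% | 6–7% | 7–11% (reversed) |
| 50% | 12–18% | 5% | 11–17% (reversed) |

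Reversed means against the hypothesis. With half attendance the cells span 5 to 36%.

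**Step 5: after removing pre-scan events.** Starting at RBUS with exact dates, the log-rank test rejects in 4.8 to 5.8% and the chi-square in 4.5 to 5.4%. A separate simulation kept time from CT with delayed entry at the scan. It assumed normal jets in 40% before and 90% after passage or treatment, and net 42-day surgery of 10 or 25%. Rejection was about 20 to 40% before the change and 4 to 6% after.

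**The case against.** **The clock is partly answered elsewhere.** Sections 5.2, 5.3 and 5.5 all count from CT, and 5.3 places the calls after RBUS. That stands, and it narrows the gap to events between CT and scan. It does not close it: 5.3 keeps the CT origin, and its record review has no lower date limit.

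**Section 6.0.** A reader might infer a post-scan outcome window from "from the time of the study RBUS to day 42 post diagnostic CT". That sentence concerns reportable events only and says nothing about passage or surgery as outcomes.

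**Appendix A.** A reader might also infer a flat contradiction, because the schedule carries the heading "Within one day of diagnostic CT". The table's columns are misaligned in the available text, so this must be checked against the original table.

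**Few such patients may be scanned.** Consent follows the CT diagnosis and, even after contact by phone or mail, requires a meeting: "This will not replace the face-to-face consent discussion the research team will have with the patient prior to signing the consent form". This makes early scans plausible, and patients whose stone has gone may be less likely to attend. It bars none of them, and remote contact allows delay.

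**The large figures are extremes.** The 18 to 38% needs evenly spread scans, every passed stone reading as Group III, and full attendance. The 32 to 51% also needs treated sides never to read as Group III. Neither is a forecast, and the documents support none of these inputs.

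**Further adjustment.** A reader might want the CT-to-scan interval as a covariate, or a repeat limited to 32 days after RBUS. With one group scanned 3 or 5 days later on average, the restricted chi-square still rejects in 4.5 to 5.5%, so neither is needed.

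**Conclusion.** The omission is certain: as written, the plan lets events before the scan count as outcomes the scan predicted. Its effect is conditional. For time to passage, the bias runs toward the protocol's hypothesis if cleared ureters tend to read as Group III. False rejection is then about 5 to 8% in the mild case (70% read as Group III, half attendance) and 18 to 38% in the extreme case. It is about 5% if jets do not recover or all scans fall within one day. A reader might infer that the intervention comparison is also biased toward the hypothesis. That does not follow, because the direction depends on how passed and treated sides read, which the documents do not say. This should be fixed because the change is cheap and settles an analysis choice before results are seen. Confidence in the size is moderate at best, because every rate used is an assumption.

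**What to change.** In 7.3:

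- Define the primary predictive set as patients with neither passage nor surgical intervention (as listed in 5.3) before RBUS.
- For Kaplan-Meier and Cox, keep time from CT with delayed entry at the RBUS date.
- In the chi-square and logistic analyses, count only interventions after RBUS, ending at day 42 after CT.
- Report patients resolved before the scan separately, and keep the full cohort from CT for the natural-history objective.
- Classify patients from data that 5.2 already records (stone presence at RBUS, passage date, time to surgery), and ask at the scan whether the stone has passed.

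Check the RBUS window in 5.2 against the original Appendix A table and reconcile them if they differ.

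**Cost with the 10-day window fully used.** Through passage alone, 8 to 17% of patients leave the primary set (4 to 9% with half attendance). Adding intervention as assumed in step 4, combined 42-day resolution is 80 or 90%, and the step 1 formula gives 17 or 23%. Interventions lost per 100 patients are 16.9 × 30/80 = 6.3 of 30, 23.0 × 20/90 = 5.1 of 20, or 23.0 × 10/90 = 2.6 of 10, which is about 21 to 26%.

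For an assumed hazard ratio of 2, power for passage falls from 68/82/88% with all scans on day 0 to 60/74/77%, a loss of 8 to 11 points. Power for intervention also falls; its size was not calculated. Time at risk after the scan varies from 32 to 42 days. Misdated passages leave some bias: if 25% are dated late, rejection is 5.1 to 6.0%; if 50%, 6.8 to 7.6%.

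With a one-day window these costs are small: about 1 to 2% of patients leave through passage, and passage power falls by about 1 point or less. The rule should still be stated.
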